## 7.3 LOST TO FOLLOW-UP

A participant will be considered lost to follow-up if he or she fails to return for 2 scheduled visits and study staff are unable to contact the participant after at least 3 attempts.

The following actions must be taken if a participant fails to return to the clinic for a required study visit:

- The site will attempt to contact the participant, reschedule the missed visit within 2 weeks, counsel the participant on the importance of maintaining the assigned visit schedule and ascertain if the participant wishes to and/or should continue in the study
- Before a participant is deemed lost to follow-up, the investigator or designee will make every effort to regain contact with the participant (where possible, 3 telephone calls and text messages and, if necessary, a certified letter to the participant's last known mailing address or local equivalent methods). These contact attempts will be documented in the participant's medical record or study file.

- Should the participant continue to be unreachable, he or she will be considered to have withdrawn from the study with a primary reason of lost to follow-up

## 8 STUDY ASSESSMENTS AND PROCEDURES

### 8.1 ENDPOINT AND OTHER NON-SAFETY ASSESSMENTS

Follow-up data will be collected at 3 months, 6 months, and 12 months.

### 8.2 SAFETY ASSESSMENTS

n/a

### 8.3 ADVERSE EVENTS AND SERIOUS ADVERSE EVENTS

#### 8.3.1 DEFINITION OF ADVERSE EVENTS

This protocol uses the definition of adverse event from 21 CFR 312.32 (a): any untoward medical occurrence associated with the use of an intervention in humans, **whether or not considered intervention-related**.

#### 8.3.3.1 SEVERITY OF EVENT

For adverse events (AEs) not included in the protocol defined grading system, the following guidelines will be used to describe severity.

- **Mild:** Events require minimal or no treatment and do not interfere with the participant's daily activities.
- **Moderate:** Events result in a low level of inconvenience or concern with the therapeutic measures. Moderate events may cause some interference with functioning.
- **Severe:** Events interrupt a participant's usual daily activity and may require systemic drug therapy or other treatment. Severe events are usually potentially life-threatening or incapacitating.

#### 8.3.2 ADVERSE EVENT REPORTING

The PI will be responsible for reporting AEs according to policies and procedures.

## 9 STATISTICAL CONSIDERATIONS

### 9.1 STATISTICAL HYPOTHESES

- Primary Efficacy Endpoint(s):

The primary outcome is change in glycemic control (A1C). To test Aim 1, a linear mixed effects regression model will be used to estimate the effect of intervention over time on glycemic control (A1C).

- Secondary Efficacy Endpoint(s):

Our secondary outcomes are diabetes distress, coping, and diabetes management. To test Aim 2, separate linear mixed effects regression models will be used to estimate the effect of the intervention over time on diabetes distress (PAID-T), coping (RSQ), and diabetes management (P-SCI, SCI, Checks/Day). Qualitative methods will be used to code data from the secondary CGM interview study into appropriate themes that then guide analysis.

### 9.2 SAMPLE SIZE DETERMINATION

**Power Analysis:** We plan to enroll 200 adolescent-parent dyads and conservatively assume a 15% dropout rate, leaving 170 subjects for analysis. Power calculations for the repeated-measures design were conducted using a variety of statistical simulations for each of the outcomes. Inputs into the simulation study, based on preliminary data from 46 subjects measured 3 months apart, were baseline mean, baseline standard deviation, and correlation between baseline and 3-month measurement. Table 3 summarizes the effect sizes that we will have at least 90% power to detect at a 0.05 significance level.

### 9.3 STATISTICAL ANALYSES

#### 9.3.1 General Approach

Outcomes will be measured at up to four time-points per subject (baseline, 3 months, 6 months, and 12 months), so we will use time, treatment group and the interaction of treatment with time serving as the main explanatory variables. Such a model will allow us to test for any differences between treatment and control groups at 3, 6 or 12 months while accounting for baseline values. While the randomized block design should minimize confounding, we will adjust for age, sex, and race/ethnicity to improve precision. The results from the adjusted and unadjusted models will be compared with respect to their estimates of the treatment effects. We will include a random intercept to account for within-subject correlation arising from taking repeated measurements on the same subject over time. The error structure of the model is assumed to be compound symmetric, and the validity of this assumption will be examined by computing Akaike Information Criteria against other common structures. Subjects will

be included in the analysis if they have an outcome measured at baseline and at least one outcome measured at 3, 6 or 12 months.

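### Adjusting for baseline A1C would estimate the 3-month effect more precisely, at almost no cost, than the treatment-by-time contrast that section 9.3.1 appears to plan

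*Combined protocol and SAP*

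**What the plan says.** Section 9.3.1 (General Approach) of the combined protocol and SAP treats baseline as one of four outcome time points. The model has "time, treatment group and the interaction of treatment with time serving as the main explanatory variables", plus a random intercept, and "The error structure of the model is assumed to be compound symmetric", to be checked by AIC against other structures. The section says that this model can "test for any differences between treatment and control groups at 3, 6 or 12 months while accounting for baseline values". It names no baseline covariate, no shared baseline mean and no covariate-by-time term.

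On covariates it says "we will adjust for age, sex, and race/ethnicity to improve precision", and then "The results from the adjusted and unadjusted models will be compared" with respect to the treatment effect. Participants enter the analysis "if they have an outcome measured at baseline and at least one outcome measured at 3, 6 or 12 months".

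Section 9.1 defines the primary outcome as change in A1C, and the synopsis (1.1) puts the primary endpoint at 3 months. Section 9.2 lists as simulation inputs "baseline mean, baseline standard deviation, and correlation between baseline and 3-month measurement", taken from 46 pilot subjects.

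**The concern.** Taken together, these sections point to the 3-month treatment-by-time term as the primary contrast: the difference between arms in mean change from baseline, with each arm's baseline mean estimated freely. Two efficiency consequences follow.

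First, a change contrast subtracts the whole baseline value, whereas regression on baseline subtracts only as much as the correlation justifies. The first is noisier unless the regression slope happens to be 1.

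Second, a covariate entered as a main effect shifts all of a participant's visits by the same amount, so it drops out of a change contrast. The precision that is the stated reason for including the covariates would not appear, and the planned adjusted-versus-unadjusted comparison would show near agreement whatever the covariates do.

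At stake is the precision of the primary estimate, using data that will be collected anyway.

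**Working it through.** **Inputs.** From 9.2: 200 dyads, 15% dropout, 90% power, significance level 0.05 (two-sided assumed). From 4.1: 1:1 allocation. Assumed: ρ, the 3-month SD, the size of the covariate effects, and time as a categorical factor. The Table 3 effect sizes are not in the text supplied, so they cannot be recomputed.

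**Plan's own figure.** 200 × (1 − 0.15) = 170, which reproduces. This is taken as 85 per arm.

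**Step 1: equal SDs (σ), complete data.**

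- Planned change contrast: variance = 2 × 2(1 − ρ)σ²/85.
- Baseline-adjusted, or one baseline mean for both arms: variance = 2(1 − ρ²)σ²/85.
- Ratio = (1 + ρ)/2, so the reduction forgone is (1 − ρ)/2.

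At ρ = 0.7 these are 4 × 0.3/85 = 0.01412σ² and 2 × 0.51/85 = 0.01200σ², a 15% reduction. Generalised least squares over all four visits gives the same values. The effect detectable with 90% power is (1.960 + 1.282) × SE (normal approximation). The equivalent number analysed is 170 × 2/(1 + ρ).

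| ρ | Variance forgone | Equivalent number analysed | Detectable effect (SD), planned → adjusted | Power after adjustment, where planned power is 90% |
|---|---|---|---|---|
| 0.5 | 25% | 227 | 0.497 → 0.431 | 96.3% |
| 0.7 | 15% | 200 | 0.385 → 0.355 | 94.0% |
| 0.8 | 10% | 189 | 0.314 → 0.298 | 92.7% |
| 0.9 | 5% | 179 | 0.222 → 0.217 | 91.4% |

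**Step 2: missing visits.** With each follow-up visit missing at random with probability 0.15, the adjusted/planned variance ratios at the same four values of ρ are 0.775, 0.866, 0.911 and 0.955, against 0.75, 0.85, 0.90 and 0.95 with complete data. Simulated trials with estimated covariances (600 per setting) gave mean model-based ratios of 0.778, 0.869 and 0.914 for the baseline-covariate model at ρ = 0.5, 0.7 and 0.8. Rejection under the null was 4.7% to 5.8% (Monte Carlo SE about 0.9 points).

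**Step 3: unequal SDs.** With s = 3-month SD / baseline SD, the gain is (1 − ρs)²/(1 + s² − 2ρs). At ρ = 0.7:

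- s = 0.8: 0.1936/0.52 = 37%
- s = 0.9: 0.1369/0.55 = 25%
- s = 1.0: 0.09/0.60 = 15%
- s = 1.1: 0.0529/0.67 = 8%
- s = 1.2: 0.0256/0.76 = 3%

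The expression is a square over a variance, so it is never negative. Estimating the slope costs about 1/170 = 0.6% of variance.

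**Step 4: covariates.** Assume two binary covariates, each shifting A1C by 0.5 SD at every visit, so that R² = 2 × 0.25 × 0.25 = 0.125.

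- Planned contrast: no change with complete data, because the shift is the same at baseline and 3 months and subtracts out. With 15% of visits missing, the variance ratios are 0.9981, 0.9992 and 0.9995 at ρ = 0.5, 0.7 and 0.8, a gain of 0.2% or less.
- After baseline adjustment: the variance ratio is (1 − R²)[1 − ((ρ − R²)/(1 − R²))²]/(1 − ρ²) = 0.952, 0.975 and 0.984, which cuts the SE by 2.4%, 1.3% and 0.8%.

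**Step 5: why the shared-baseline version should not keep compound symmetry.** Its 3-month estimate subtracts the baseline difference times the fitted common correlation b. The variance ratio to the planned contrast is then (1 + b² − 2bρ)/(2(1 − ρ)). If the true 3-month ρ is 0.8 and correlations fall off at later visits, so that b is 0.7, 0.6 or 0.5, the ratio is 0.93, 1.00 or 1.13. The gain can vanish or reverse.

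**The case against.** The strongest reply is that the contrast is inferred. Section 9.3.1 speaks of differences at any of three visits, section 9.1 of an effect over time, and section 3 lists all four time points for the primary objective. The listed terms are called main explanatory variables, which need not be exhaustive, and the section does say that baseline values are accounted for. If the test were the raw between-arm difference at a visit, main-effect covariates would help. This stands as a limit: the point rests on the natural reading. But the sentence about baseline describes the interaction model just set out, and a raw visit difference would not account for baseline. If a baseline covariate is intended, the section should say so.

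The gain is also of unknown size and could be negligible at high ρ or with a larger SD at 3 months. That stands too.

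A reader might infer that the planned analysis is biased, or that the trial has less power than stated. The documents support neither. Under randomisation the change contrast is unbiased, and 9.2 does not say which contrast was simulated. Nor does it follow that covariates can never help, or that adjustment recovers a substantial gain from them. The exact cancellation needs complete data, main effects only and the change contrast, and the gain from covariates after adjustment is small.

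**Conclusion.** This is a cheap improvement, not an error. On the natural reading of 9.3.1, the primary 3-month estimate gives up a share (1 − ρ)/2 of its variance if the SDs are equal at baseline and 3 months, which is 5% to 25% for ρ from 0.9 to 0.5 and slightly less with missing visits. With unequal SDs the gain can be larger or close to nothing. The sponsor can settle the size from the pilot data, since ρ was an input to the power simulations. The covariate result does not depend on ρ with complete data: as main effects, the covariates leave the planned contrast unchanged, and almost unchanged with missing visits, so the adjusted-versus-unadjusted comparison will say little.

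**What to change.** In 9.3.1, state that the primary estimate is the 3-month treatment difference from a model of 3-, 6- and 12-month A1C with visit, treatment-by-visit, baseline A1C-by-visit, and age, sex and race/ethnicity as main effects. Use an unstructured within-subject covariance in place of the random intercept. Equivalently, keep baseline as an outcome with one mean shared by both arms (no treatment main effect) and an unstructured covariance, again without the random intercept and not with compound symmetry. In either form the AIC comparison of error structures is no longer needed for the primary model.

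The same form can be used for the secondary outcomes, where the size of the gain is unknown. It may be smaller for diabetes distress, because participants are selected on the PAID-T (4.2, 5.1) and its baseline spread may be narrowed. As an illustration, with an assumed slope of 0.7 and residual variance of 0.51, the gain is 0.09/0.60 = 15% at baseline variance 1, but 0.036/0.546 = 6.6% at baseline variance 0.4.

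The cost is revised SAP wording and model code, a few more parameters, and about 0.6% of variance for estimating the slope. No new data are needed, and no participant is lost, because the inclusion rule already requires a baseline value.

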### 3 OBJECTIVES AND ENDPOINTS

OBJECTIVES	ENDPOINTS	JUSTIFICATION FOR ENDPOINTS	PUTATIVE MECHANISMS OF ACTION
Primary			
Glycemic Control (HbA1c)	Baseline, 3 months, 6 months, 12 months	Corresponding with diabetes clinic visits	
Secondary			
Diabetes Distress, Positive Affect, Coping, Diabetes Management, Quality of Life, Family Conflict, Resilience	Baseline, 3 months, 6 months, 12 months		
Tertiary/Exploratory			
Demographics (adolescent age, sex), use of diabetes devices	Baseline		

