## 4 STUDY DESIGN

### 4.1 OVERALL DESIGN

To test the effects of the proposed intervention, we will recruit a sample of 200 adolescents with T1D and their parents from two clinical sites (Vanderbilt University Medical Center and Children's National Medical Center, 100 dyads from each site). Adolescents will be eligible if they (1) are between the ages of 13-17; (2) have been diagnosed with T1D for at least 12 months; (3) score above the clinical cutoff on a screening tool for diabetes distress; and (4) speak and read English. The sampling goal for this study across the two sites is 68% white, 10% Hispanic, 16% Black, and 6% Asian, with equal numbers of boys and girls, in line with recent studies conducted in these settings.

If the adolescent is eligible, the RA will obtain informed consent/assent, and the adolescent and his/her parent will complete the baseline measures. Participants will then be randomly assigned to one of two conditions: Positive Affect and Education (n=100) or Education only (n=100). Randomization will be stratified by use of diabetes devices (insulin pump and CGM), to avoiding confounding effects. A computer program will generate the randomization scheme.

After completing the exit interview, participants who use/have used a continuous glucose monitor (CGM) will be offered the opportunity to participate in a secondary study to discuss the role of CGM in their diabetes management.

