### 6.3 MEASURES TO MINIMIZE BIAS: RANDOMIZATION AND BLINDING

The randomization scheme will be determined by the biostatistician, and adolescents will be stratified by diabetes device use (insulin pumps, continuous glucose monitors).

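### Randomization is stratified by pump and CGM use, but the main model omits both factors; adding them by visit may gain a little power at almost no cost

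*Combined protocol and SAP*

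**What the plan says.** Section 4.1 states: "Randomization will be stratified by use of diabetes devices (insulin pump and CGM), to avoiding confounding effects". Section 6.3 repeats that "adolescents will be stratified by diabetes device use (insulin pumps, continuous glucose monitors") and names no other stratification factor.

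Section 9.3.1 sets out the main model. Its core is "so we will use time, treatment group and the interaction of treatment with time serving as the main explanatory variables". It has a random intercept per participant, and "The error structure of the model is assumed to be compound symmetric", with other structures to be compared by AIC. On covariates it says "we will adjust for age, sex, and race/ethnicity to improve precision". An unadjusted model is to be fitted for comparison. No device term appears in either model.

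The endpoint table in Section 3 lists "Demographics (adolescent age, sex), use of diabetes devices" at baseline, under tertiary/exploratory. Section 9.3.2 uses device use only as a possible effect modifier.

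**The concern.** Stratifying on a factor makes the arms nearly equal on it, so the treatment comparison varies less from trial to trial than under simple randomization. The analysis reflects that reduction only if the factor is in the model. If it is left out, the variance it explains stays in the residual, the reported standard error is larger than the true one, and the test rejects less often than its nominal level.

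The plan adjusts for three covariates to gain precision, yet leaves out the two factors that the design singled out. The question is how much that costs.

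The key quantity is the treatment-by-time contrast, which is a comparison of changes from baseline. If device use shifts a participant's A1C by the same amount at every visit, the random intercept absorbs the shift and the omission has no effect. It matters only if device use predicts **change** in A1C.

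**Working it through.** **Inputs from the documents.** Section 4.1 gives 1:1 allocation, 100 per arm. Section 9.2 plans to "conservatively assume a 15% dropout rate, leaving 170 subjects for analysis", and 200 × 0.85 = 170, or 85 per arm. The same section gives at least 90% power at a 0.05 significance level. Its simulation inputs are "baseline mean, baseline standard deviation, and correlation between baseline and 3-month measurement"; no device adjustment is listed, so the 90% does not appear to depend on one. Section 9.3.2 gives 60% pump use in pilot data.

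**Assumptions.** The test is two-sided. R² is the share of the variance of the change contrast that the strata explain; no document gives it, so 0%, 2%, 5% and 10% are shown. The simulation takes CGM prevalence as 50%.

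**Anchor.** The 90% cannot be reproduced independently, because the effect sizes and pilot SD and correlation are not in the available text. It is taken as given at R² = 0. The noncentrality is then 1.9600 + 1.2816 = 3.2415. With 85 per arm this corresponds to 3.2415 × √(2/85) = 0.497 SD of the analysed change.

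**Formulas.** Under stratified randomization the true SE is the planned SE × √(1 − R²). Let r be the ratio of reported to true SE when the strata are omitted.

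- (a) Planned model: random intercept, compound symmetry, four visits, device shift constant after baseline. A shift d gives the pattern (0, d, d, d). Its within-person sum of squares is 3d² − 9d²/4 = 3d²/4, or d²/4 per degree of freedom (3 per person). The change contrast has twice the residual variance, so half of the device variance enters its estimated variance: r = √(1 + 0.5·R²/(1 − R²)).
- (b) Contrast-specific SE, as under an unstructured covariance if AIC favours one: r = 1/√(1 − R²).
- Type I error without strata = 2Φ(−1.96·r).
- Power without strata = Φ(3.2415/√(1 − R²) − 1.96·r).
- Power with strata = Φ(3.2415/√(1 − R²) − 1.96).

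**Closed-form results.**

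| R² | Model | SE overstated | Type I error, no strata | Power without | Power with | Gain (points) |
|---|---|---|---|---|---|---|
| 0% | both | 0% | 5.0% | 90.0% | 90.0% | 0 |
| 2% | (a) | 0.5% | 4.9% | 90.4% | 90.6% | 0.2 |
| 5% | (a) | 1.3% | 4.7% | 91.0% | 91.4% | 0.4 |
| 10% | (a) | 2.7% | 4.4% | 92.0% | 92.7% | 0.8 |
| 2% | (b) | 1.0% | 4.8% | 90.2% | 90.6% | 0.3 |
| 5% | (b) | 2.6% | 4.4% | 90.6% | 91.4% | 0.8 |
| 10% | (b) | 5.4% | 3.9% | 91.2% | 92.7% | 1.6 |

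Gains are taken from unrounded powers.

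**Simulation.** There were 40,000 trials per cell, with 200 randomized in blocks of 4 within four device strata, 170 retained at random, and the 3-month contrast tested. The Monte Carlo SE is about 0.1 point for type I error and 0.15 point for power.

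| R² | Gain (a), points | Gain (b), points | Type I error without strata (a) | Type I error without strata (b) |
|---|---|---|---|---|
| 0% | −0.1 | 0.0 | 5.2% | 5.2% |
| 2% | 0.1 | 0.3 | 5.0% | 4.8% |
| 5% | 0.4 | 1.0 | 4.6% | 4.3% |
| 10% | 0.8 | 1.7 | 4.7% | 4.2% |

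The formulas therefore slightly overstate the conservatism at R² = 10%.

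**Which terms matter.** Random-intercept models were fitted to 15 simulated data sets of 170 complete participants, with devices affecting change. The mean SE of the treatment-by-3-month term was 0.1320 without device terms, 0.1320 with pump and CGM main effects, and 0.1293 with device-by-visit terms. Only the visit interactions reduce it.

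**Degrees of freedom.** Within-subject degrees of freedom are 3 × (170 − 2) = 504 without device terms, 3 × (170 − 4) = 498 with two binary factors by visit, and 3 × (170 − 5) = 495 with four pump-by-CGM cells. The critical t moves from 1.96468 to 1.96474 or 1.96477, which costs 0.001 to 0.002 power points.

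**The case against.** The strongest reply is that nothing goes wrong if the plan is left alone. The error is conservative, the estimate is unbiased, and power stays at or above 90%. The gain rests on an R² that no document supplies, and it vanishes if devices predict only the level of A1C. Under the model actually planned it is below one power point, and at R² = 2% the simulated gain is smaller than the Monte Carlo error of a single power estimate. Simply adding device to the existing covariate list would achieve nothing. The sizes are also worked out only for A1C at 3 months. All of this stands, and it limits the point to a minor refinement.

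A further reply is that the plan already deals with devices, through the moderator analysis and the comparison of adjusted with unadjusted models. That does not stand. The moderator models are exploratory and ask a different question, and neither model in 9.3.1 contains a device term.

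**Conclusion.** The concern holds and is minor. The main model leaves out the two factors on which randomization is stratified. If they explain 2% to 10% of the variance in A1C change, the planned compound-symmetric model forgoes about 0.2 to 0.8 power points by formula (0.1 to 0.8 by simulation). With a contrast-specific SE the loss is 0.3 to 1.6 points by formula (0.3 to 1.7 by simulation). If they explain none, there is no loss. These figures assume a two-sided test, an anchor of 90% power at R² = 0, 15% attrition at random, and, for the compound-symmetric formula, a device effect that is constant after baseline. No conclusion of the trial would be unsafe under the present text; the case for change is that the improvement is almost free.

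**What to change.** Add one sentence to Section 9.3.1: the primary and secondary models include baseline pump and CGM use, coded exactly as in the randomization, each with its interaction with visit. The interactions are essential when baseline A1C is one of the repeated outcomes. If the sponsor instead means to condition on baseline A1C as a covariate, device main effects would also contribute; the section's wording on baseline allows either reading and should say which applies.

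The sentence should also state whether the strata are two binary factors or four pump-by-CGM cells, since Sections 4.1 and 6.3 do not say. That means 8 or 12 parameters per model over four visits. No new data are needed, because device use must be known before a stratified randomization and is listed at baseline. Fixing the terms before unblinding also removes any later choice about including them.

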Non-Compliance/ Continuing Review 5/17/2021	Many participants were recruited and enrolled through remote method due to Covid-19 restrictions. The HRPP allowed this change without prior approval due to extenuating circumstances. This protocol deviation detailed the covid-related changes we made.	Covid changes in this protocol deviation included the following: Rather than approaching patients in clinic, we used Epic to track which patients were attending appointments through telehealth and called them to recruit for the study. Eligibility surveys were sent through email provided by the participant at the time of the call. – Rather than enrolling participant in the clinic, we enacted the same study protocols over zoom and sent study surveys through email.
Measures 8/26/2021	We added questions to the parental COVID-19 supplemental measure. We are asking participants if any adults (18+) and children (12-17) have been vaccinated in their household. Also, we are asking if their child has seen their	To remain current on how COVID-19 is affecting study participants, we added additional questions to our COVID-19 survey measure related to COVID-19 vaccination status and the use of telehealth clinic visits. Many COVID-19 restrictions currently in place (locally and

	
diabetes provider via telehealth visit since this could impact their quality of care and one of our specific study aims (glycemic control). These changes were only applied to the parent surveys.
 
domestically) are dependent on vaccination status, so these questions will help us to interpret findings related to the effects of COVID-19 on diabetes management and mood.

--	---

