Retention & Follow-Up: Efforts will be made to maximize retention across trial assessments. These include providing study retention items (e.g., keychain flashlights, laptop decals with the study logo), sending birthday cards to trial participants, and verifying contact information, including email addresses and phone numbers, at each assessment point. As in previous studies, we will attempt to collect follow-up data in person during regularly scheduled clinic appointments. Prior to their scheduled appointment, families will be reminded of the visit and asked to come early or stay after their appointment. If families cancel or do not show for their appointments, we will email and text a unique link to the REDCap survey and continue to follow up by phone and email until surveys are completed. We will give the family the option of doing a Coremedica HemaSpot-SE HbA1c kit at home if they are unable to come into the clinic to get a point of care A1c test. If families are not responsive, we will send a paper packet with a self-addressed, stamped envelope. These methods have resulted in excellent retention rates (91-98%) in our pilot studies. We will actively work towards maintaining families' participation in data collection regardless of their engagement in the text messages so that intent-to-treat analyses may be conducted. We are conservatively planning for a ~15% attrition rate based on data from our pilot studies to protect against overestimation.

Incentives. In order to promote the completion of trial measures at all assessment points, participants will be compensated for their time at each data collection, with increasing compensation (\$20, \$25, \$30, \$30) to improve retention. In addition, participants will receive \$10 for participating in a qualitative exit interview at the 3-month data collection. Participants who complete the secondary study (interview describing their CGM use) will receive an additional \$30 gift card.

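### The analysis set depends on having follow-up data, so it is an available-data set rather than all randomised, and it can bias the A1C contrast if early loss differs by arm

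*Combined protocol and SAP*

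**What the plan says.** Section 9.3.1 models up to four measurements per subject, baseline among them, with time, treatment group and their interaction, a random intercept and a compound-symmetric error structure. It then limits the data: subjects are "included in the analysis if they have an outcome measured at baseline and at least one outcome measured at 3, 6 or 12 months".

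Section 5.3 commits to keeping families in data collection "regardless of their engagement in the text messages so that intent-to-treat analyses may be conducted". Section 9.2 plans for the loss: "We plan to enroll 200 adolescent-parent dyads and conservatively assume a 15% dropout rate, leaving 170 subjects for analysis". Its power statement refers to "effect sizes that we will have at least 90% power to detect at a 0.05 significance level".

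Section 9 names no analysis population, states no missing-data assumption, and gives no sensitivity analysis for those whom the rule removes.

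**The concern.** Baseline is one of the modelled outcomes, so a likelihood fit of the plan's own model can use anyone with a single measured value. The inclusion rule is not needed to fit the model, and it removes two groups.

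- **Baseline only.** These participants are removed because of what happened after randomisation. Their baseline values are what would let the model correct for loss that depends on baseline.
- **Follow-up only.** These participants carry direct information on the outcome, and removing them costs precision.

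The first group matters more. The arms differ in contact: one receives texts five days a week, gift-card codes and parental affirmations, while the other receives a contract and a packet. Early loss could therefore relate to baseline A1C differently by arm. If it does, the retained groups start from different baselines, regress toward the mean by different amounts, and show a difference in change with no true effect behind it.

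**Working it through.** **1. The plan's own figure.** Section 9.2 gives 200 dyads and 15% dropout: 200 × (1 − 0.15) = 170, which reproduces. The rule therefore removes at most 200 − 170 = 30 of the planned dropouts. It reaches 30 only if every dropout has no follow-up at all, because anyone with one value at 3, 6 or 12 months is kept. The detectable effects cannot be reproduced, since Table 3, the SD and the correlation are not in the available text.

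**2. Assumptions (not in the documents).** A1C SD σ = 1.5 to 2.0. Baseline to follow-up correlation ρ = 0.6 to 0.8. The probability of having no follow-up is logistic in standardised baseline Z, with log-odds slope 1 or 1.5 per SD in one arm and 0 in the other, and the same overall loss in both arms. One follow-up is considered, with no true effect.

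**3. Bias formula.** With baseline means free by arm, the group-by-time estimate in the restricted set is the difference between arms in mean change. In an arm with overall loss L and loss probability p(Z), retained participants start lower by δ = E[Z·p(Z)] / (1 − L), in SD units. Their mean change is then shifted by (1 − ρ)·σ·δ. With δ = 0 in the other arm, that shift is the bias. With equal dependence in both arms the two shifts cancel.

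**4. Numbers in** (δ by numerical integration; bias in A1C points):

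| Loss | Slope | δ | ρ 0.8, σ 1.5 | ρ 0.8, σ 2.0 | ρ 0.6, σ 1.5 | ρ 0.6, σ 2.0 |
|---|---|---|---|---|---|---|
| 5% | 1 | 0.047 | 0.014 | 0.019 | 0.028 | 0.038 |
| 5% | 1.5 | 0.065 | 0.019 | 0.026 | 0.039 | 0.052 |
| 15% | 1 | 0.133 | 0.040 | 0.053 | 0.080 | 0.106 |
| 15% | 1.5 | 0.175 | 0.053 | 0.070 | 0.105 | 0.140 |

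For example, the last cell is (1 − 0.6) × 2.0 × 0.175 = 0.140. The ranges are 0.01 to 0.05 at 5% loss and 0.04 to 0.14 at 15%.

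**5. What removes the bias.** In a large simulation of the 15%, slope 1.5, ρ = 0.6 case, the change contrast in the restricted set was off by 0.070 SD. Using every observed baseline value with free baseline means brought it to zero within simulation error. So did adjusting for baseline in the restricted set.

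**6. Precision.** Take 85 complete participants per arm, compound symmetry, and the variance of the 3-month group-by-time effect from the generalised least squares information matrix. Add back 30 participants. Variance relative to the 170-subject set:

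| The 30 added | Baseline means | ρ 0.5 | ρ 0.7 | ρ 0.8 |
|---|---|---|---|---|
| Baseline only | Free | 0.963 | 0.977 | 0.985 |
| Baseline only | Common | 1.000 | 1.000 | 1.000 |
| Follow-up only | Free | 0.944 | 0.947 | 0.948 |
| Follow-up only | Common | 0.878 | 0.902 | 0.917 |

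Baseline-only participants reduce variance by 0 to 4%, and follow-up-only participants by 5 to 12%.

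**The case against.** **Intent to treat.** A reader might infer that the rule contradicts the intent-to-treat commitment. The documents do not support that. The section 5.3 sentence mainly concerns teens who do not engage with the texts. Section 9.3.1 excludes no one for non-engagement and moves no one between arms, and section 9.2 openly budgets for the smaller set. The gap is in completeness of the set, not in analysis as assigned.

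**Power.** A reader might also infer that the rule costs the trial its 90% power. It is not shown to: that figure is already based on 170 subjects, so up to 30 exclusions are allowed for.

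**Missing baselines.** It is tempting to infer many missing baseline A1C values from the change log, which records that "Many participants were recruited and enrolled through remote method due to Covid-19 restrictions". That is conjecture. Section 6.1 randomises after baseline data are complete, the schedule of activities places A1C at Visit 1, and the log's remark on unobtainable point-of-care values is the reason given for adding home kits. Section 5.3 describes those kits under follow-up and does not say whether they serve enrolment, so some gaps remain possible, but no rate is given.

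**Source of the bias.** The bias needs the free-baseline contrast as well as the rule; baseline adjustment in the restricted set also removes it. This stands. However, section 9.3.1 names only age, sex and race/ethnicity as adjusters and states no baseline constraint, so the protection is not written into the plan.

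**Size.** The 15% case is generous. Section 5.3 cites pilot retention of 91 to 98%. At 2% to 9% loss, even slope 1.5 gives only about 0.01 to 0.09 A1C points. This also stands.

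**Conclusion.** The point holds in a limited form. The rule conditions on post-randomisation data, yields an available-data set, and discards values that the plan's own model can use. The possible bias in the A1C change contrast is about 0.01 to 0.05 points at 5% loss of all follow-up. At 15% it is 0.04 to 0.14, an upper case because that loss rate assumes that no dropout has any follow-up value.

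These figures rest on the assumed SD, correlation and one-arm slopes, on free baseline means, and on loss depending on baseline A1C differently by arm. With equal dependence the bias is zero. Nothing in the documents shows that differential loss occurred or is expected. The precision gain is nil to small for baseline-only participants and clearer for follow-up-only participants, whose number is unknown and may be small.

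**What to change.** Replace the inclusion sentence in section 9.3.1 with: *all randomised participants with at least one measured value of the outcome at baseline, 3, 6 or 12 months are analysed in the arm assigned, by likelihood-based mixed model using every observed value, with baseline in the outcome vector and a common baseline mean across arms, assuming data are missing at random.* Keep the current rule as a sensitivity analysis.

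The common baseline mean guards against the bias even among those with follow-up. The wider set brings the analysis as close to all randomised as the data allow and recovers any follow-up-only participants. Someone with no measured value of an outcome still contributes nothing to that model.

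The cost is one sentence in the plan and one extra model run, with no new data, visits or participant burden.
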